Patients who have had Cognitive Behavioral Therapy, Biofeedback or other Relaxation Therapy in the past year; Cognitive deficit or other physical problem with the potential to interfere with behavioral therapy; Alcohol or other substance abuse as determined by self-report or prior documentation in the medical record; Unable or unwilling to follow a treatment program that relies on written and audio recorded materials; Not having a smartphone.

Vulnerable Subjects

N/A

Methods & Procedures

Methods & Procedures

Aim 1 has been completed. We are proceeding with the Methods & Procedures for Aim 2:

Aim 2: Examine the impact smartphone-based PMR on migraine quality of life, frequency, intensity, and disability. The primary outcome is to assess whether use of PMR in the ED improves migraine quality of life (MSQv2) at 3 months post ED-discharge (or post enrollment date if recruited post ED discharge). All subjects (N=90) will complete a migraine quality of life assessment and track their headache frequency and intensity using our APP. The smartphone app will be used to monitor adherence.

The non-traditional Research Volunteer (RV) or Research Assistant (RA) will obtain subject consent for the study.

In the light of COVID-19 and increased participant preference for remote visits, we will also recruit subjects via telephone and electronic consent will be obtained via REDCap. Following this, the initial enrollment visit will be scheduled and completed via Webex. The followup data points will continue to be collected via followup calls or emails as approved previously.

The NYU Headache Research Program has been recognized for its solid training of pre-health students in research methods. In fact, it received the first ever City College of New York S Jay Levy Fellowship for Future Leaders Distinguished Internship Host Award (2017-2018).

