All subjects will receive follow-up phone calls or emails (from REDCap or send safe emails) at 7 days and 1, 2, 3, and 6 months after discharge. Follow-up will be assured by testing the subject's phone number in front of the subject and asking for alternative contact information. Prior studies have shown that data can be successfully obtained from subjects at 24 hours, and 1 and 3 months-post ED discharge (over 90% follow-up rates). During the calls, the RV or RA will reiterate the importance of adherence with the APP. During the 1, 2, 3 and 6 month calls or emails (from REDCap or send safe emails), they will be asked to complete the REDCap follow-up questionnaires (already part of the IRB submission with the added modification of the MSQv2). They may also receive phone calls or SendSafe emails or texts up to every 3 days if the smartphone app data indicates that they are not completing the headache diary. If benefits do not persist, future studies may add additional interventions. Throughout the study, subjects will be asked to record electronically any new and/or discontinued medications and interactions with the medical community.

The choice of calls, texts or emails came from prior subjects who participated in IRB approved study focus groups. The study team has permission from MCIT to send the following text messages (and an emailing indicating such approval is part of the submission process):

1. Please remember to use the app.
2. Hi, The RELAXaHEAD team is trying to reach you. Please call xxx-yyy-zzz [study phone number]?
3. You are due for your follow-up call/email. Please be sure to call us at xx-yyy-zzzz or respond to the email. - The RELAXaHEAD team.
4. Remember-relaxation is beneficial for your health.
5. The best way to add relaxation into your routine is to pair it with an activity you do each day. Let us know if you want to discuss how to improve your adherence with the RELAXaHEAD app.
6. Research has suggested that the more one is able to practice relaxation, the better one's health. Log into the RELAXaHEAD app when able.

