All subjects will be given a \$60 gift card incentive for participating, and will receive an additional \$1 per day they do the intervention to compensate them for study-related time and data usage costs. If they complete the intervention more than 80% of the total 60 days of the study, then the daily compensation will be doubled. In addition, they will receive \$15 gift cards for the one month and two month f/u emails/calls and \$25 gift cards for the 3 month and 6 month f/u email or phone assessments. Thus, based on the prior adherence data, the max total projected amount that participants will receive is \$200 but if they get the bonus, they could get up to \$260.

This payment is on par with other migraine smartphone studies throughout the country.

Fidelity monitoring will be conducted as in Aim 1.

Data Analysis and Data Monitoring Analysis Plan

Sample Size: The sample size was calculated for the primary outcome (Δ MIDAS) and the secondary outcome (number of headaches/30 days). A study of medication plus behavioral therapy for migraine as compared with medication alone in the outpatient setting showed that the distribution of MIDAS at baseline or 3 months was right-skewed, but the Δ MIDAS was symmetric and approximately normally distributed. Considering Δ MIDAS as the primary outcome can reduce data skewedness and improve study power. Based on the study, the standard deviation (SD) of Δ MIDAS ranges from 5 to 7. With the conservative estimate of SD=7, group sample sizes of 31 and 31 achieve 80% power to detect a clinically significant difference of 5 between the groups, assuming

group standard deviations of 5 and a significance level of 0.05 using a two-sided two-sample t-test. The emergency medicine studies had over 90% follow-up at 3 months and the electronic headache diary studies' follow-up was between 76%–80%. To accommodate potential dropout rate as high as 30%, a total of 90 subjects will be recruited.

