Quality Control: The Clinical Data Monitor will download the data from the Diary Cloud Server. From this download, standard reports including missing days or entries as well as identification of any safety concerns will be created from the downloaded database and examined and reviewed by the Clinical Data Monitor.

Measurements: Our primary outcome, the Migraine Quality of Life (MSQv2) is a validated quality of life measure. In addition, we will check the Migraine Disability Assessment Scale (MIDAS), measures disability over the past 3 months. MIDAS scores were shown to have excellent test-retest reliability, high internal consistency and high external validity using a variety of measures including diary based measures. MIDAS scores are also associated with physician judgements about the severity of headache and the need for treatment. A decrease of 3 points in the MIDAS score corresponds to a one day reduction in headache related disability per month, a clinically meaningful difference. In the Headache Management Trial, persons with headache were randomized to coordinated, guideline-based care vs. usual care. The study was designed to detect a 5-point difference in MIDAS decline between treatment arms and found a highly clinically significant 7 point decline. We will examine the change in disability scores (Δ MIDAS) defined as the difference between MIDAS scores at 3 months and at baseline.

Data Storage and Confidentiality

Each subject will be assigned a unique alphanumeric identifier for use with the app. No PHI is being given to IRODY. The alphanumeric identifiers will be unrelated to the identity of the study subjects. All clinical data/information will be entered into the RedCap database. Only the PI and the RVs/RAs will have access to the linking database.

The consent forms will be kept in a separate locked file cabinet in the Tisch ED. They will be transferred periodically to a locked cabinet at [name]. If someone were to gain illegal access to the locked filing cabinet with study data, they would have no way to link this data to any identifying information.

The research team will perform all data analyses. Data will be stored electronically in a secure research database and will be available for the research team.

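### The plan names two different primary outcomes (MSQv2 and ΔMIDAS), and its 80% power belongs only to ΔMIDAS

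*Combined protocol and SAP*

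**What the plan says.** Three places in the current text of the addendum name a primary outcome.

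- **Methods & Procedures, Aim 2:** "The primary outcome is to assess whether use of PMR in the ED improves migraine quality of life (MSQv2) at 3 months post ED-discharge".
- **Measurements:** "Our primary outcome, the Migraine Quality of Life (MSQv2) is a validated quality of life measure". MIDAS then follows as a further measure: "In addition, we will check the Migraine Disability Assessment Scale (MIDAS".
- **Data Analysis and Data Monitoring, Sample Size:** "The sample size was calculated for the primary outcome (Δ MIDAS", with the headache count per 30 days as secondary. The paragraph goes on: "Considering Δ MIDAS as the primary outcome can reduce data skewedness and improve study power". The calculation is "With the conservative estimate of SD=7, group sample sizes of 31 and 31 achieve 80% power to detect a clinically significant difference of 5", and the same sentence then assumes "group standard deviations of 5 and a significance level of 0.05 using a two-sided two-sample t-test". Allowing for 30% dropout, it arrives at 90 recruited.

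The only other power calculation is for the headache count. The follow-up paragraph of Methods & Procedures describes the follow-up questionnaires as "already part of the IRB submission with the added modification of the MSQv2". The Number of Subjects section calls the study a pilot.

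**The concern.** A randomised comparison needs one outcome, fixed in advance, that decides it. Here two outcomes each have text calling them primary, and no sentence ranks them, makes them co-primary or says which governs. Either could later be reported as prespecified, with a quotation to support it.

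The sample-size justification is also detached from the outcome that Methods and Measurements name. A reader who takes MSQv2 as primary will read the 80% as applying to it, which it does not. Nor could an analyst run an MSQv2 primary analysis from this document. It does not say which domain or total score is meant or which between-group test applies, and the only change score it defines is ΔMIDAS.

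The reference to MSQv2 as an added modification suggests that the sample-size text was not updated when MSQv2 came in. That is an inference; the document does not say so.

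**Working it through.** **Inputs from the Sample Size paragraph:** ΔMIDAS difference 5; SD stated as 7 and also as 5; two-sided 0.05; two-sample t-test; 31 per arm; 80% power; 30% dropout; N=90. There are no MSQv2 inputs to take from the document.

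**1. The plan's own figure.** By normal approximation, n per arm = 2(1.960 + 0.842)² × SD² / difference².

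- SD 7: 2 × 7.849 × 49 / 25 = 30.8, so 31. Power at 31 per arm is 80.3% by normal approximation and 79.0% by t-test. The t-test itself needs 31.8, so 32.
- SD 5: 2 × 7.849 × 25 / 25 = 15.7, so 16 (17 by t-test). Power at 31 per arm is 97.2% by t-test.
- Dropout: 62 / 0.70 = 88.6, so 89, consistent with 90.

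The stated 31 per arm and 80% therefore rest on ΔMIDAS with SD 7. The SD of 5 in the same sentence does not fit them.

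**2. What the same sample offers MSQv2.** With no MSQv2 SD or difference, only standardised effects can be used (two-sample t-test, two-sided 0.05). The 80% power threshold is close to the plan's ΔMIDAS effect of 5/7 = 0.71 SD. The effect sizes below are assumptions.

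| Evaluable per arm | SD detectable at 80% | Power at 0.4 SD | 0.5 SD | 0.6 SD | 0.8 SD |
|---|---|---|---|---|---|
| 31 (planned minimum) | 0.72 | 34% | 49% | 64% | 87% |
| 40 (about 90% retained) | 0.63 | 42% | 60% | 76% | 94% |
| 45 (no dropout) | 0.60 | 47% | 65% | 80% | 96% |

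**3. Effect of adjusting for baseline MSQv2.** The effective standardised difference becomes d / √(1 − r²), where r is the correlation between baseline and 3 months. At 31 per arm and d = 0.5:

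- r = 0.3: 0.5 / 0.954 = 0.524, power 53%
- r = 0.5: 0.5 / 0.866 = 0.577, power 61%
- r = 0.7: 0.5 / 0.714 = 0.700, power 77%

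The values of r are assumed.

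**4. Ceiling on the error from a late choice.** Suppose each outcome were tested at 0.05 and the favourable one called primary. With independent outcomes the chance of at least one false positive is 1 − 0.95² = 9.75%. From the bivariate normal it is 9.1%, 8.3% and 7.0% at assumed correlations of 0.5, 0.7 and 0.9.

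**The case against.** The strongest reply is that the intention is readable. Both places that define outcomes name MSQv2, and Aim 2 lists quality of life first and disability last. On this view only the Sample Size label is out of date. The second mention of ΔMIDAS there can also be read as preferring the change score to the skewed raw MIDAS, not MIDAS to MSQv2. That reading is fair. But the first mention still calls ΔMIDAS the primary outcome outright and rests the enrolment target on it. If the label is a leftover, it still has to be corrected.

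On power, several points stand:

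- The study is a pilot, which lowers the weight of a missing power figure.
- The Sample Size paragraph cites over 90% follow-up in emergency studies, so 31 per arm is the pessimistic case.
- No power loss is demonstrated, since the detectable MSQv2 effect (0.72 SD) is almost the planned ΔMIDAS effect (0.71 SD).
- The 9.75% is a hypothetical ceiling. The plan does not set out such a procedure.

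The addendum supplements a main protocol that was not available, and MSQv2 scoring or analysis may be specified there. So the missing MSQv2 detail is claimed for this document only. The contradiction between its own sections does not depend on the main protocol.

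**Conclusion.** The concern holds. The contradiction is certain, lies in current text and is not resolved in the addendum. The 80% power is a ΔMIDAS figure that requires SD 7; MSQv2 power is unstated, not shown to be inadequate. The sample would give MSQv2 80% power, unadjusted, only for differences of about 0.72 SD at 31 evaluable per arm, or 0.63 to 0.60 SD at 40 to 45. Power at any particular MSQv2 effect, the gain from baseline adjustment and the type I error at a given correlation all rest on assumed values.

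This must be fixed because of the conflicting labels: a primary outcome chosen after results are seen cannot be credibly repaired. Pilot status does not say which outcome is primary.

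**What to change.** Before outcomes are compared by arm, name one primary outcome, with its score and 3-month time point, identically in Methods & Procedures, Sample Size and Measurements. Label the other secondary. The text favours MSQv2.

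**If MSQv2 is intended:**

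1. State the outcome and test, for example: *Primary outcome: MSQv2 [named domain or total score] at 3 months. Primary test: linear regression of the 3-month score on arm and baseline MSQv2, two-sided 0.05. ΔMIDAS and headaches per 30 days are secondary.* Another single prespecified test would also settle the point.
2. State that MSQv2 is collected at T0. The follow-up paragraph mentions it only for the later questionnaires.
3. In Sample Size, stop calling ΔMIDAS primary and write: *N=90 was sized on ΔMIDAS. For MSQv2, 31 evaluable per arm detects about 0.72 SD with 80% power before baseline adjustment. The assumed MSQv2 SD is [sponsor value], the meaningful difference is [sponsor value, justified], and the resulting power is [value].* If that power is below 80%, report it as such.
4. In the retained ΔMIDAS calculation, change the group SDs of 5 to 7, the only stated value that reproduces 31 per arm (by normal approximation; 79.0% power by t-test).

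**If ΔMIDAS is intended:** correct Methods & Procedures and Measurements instead, name its single two-sided 0.05 test, and make correction 4.

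**Cost:** wording, plus an MSQv2 SD and meaningful difference from the sponsor if MSQv2 is chosen. No added enrolment is needed or requested. For scale, 80% unadjusted power at an assumed 0.5 SD would take 64 evaluable per arm, or 128 / 0.70 = about 183 recruited, against the planned 90.

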While explaining the study, potential subjects will be assured that they will receive all of the medication for their acute headache that they would otherwise receive. Once consented, subjects will be randomized to PMR therapy or MUC. Participants will be told that either group is being tested as an enhancement to the care they typically get in the ED for headache. At the end, they will be told that they will be informed which group they were in. The RV or RA will then collect subjects' health histories (biologic variables) and baseline data in REDCap on an iPad, download the app onto subjects' smartphones, and conduct the sessions (see below). There will be fidelity monitoring.

We will be requesting the Epic Research Team for a report of the following data for patients who visited the ED for headache from 10/22/2017 to 02/18/2019:

- gender
- race
- pcp or neurology care provider
- zip codes - or region they live in
- did they have a neurologist before visiting ED
- did they have diagnosis of migraine prior to visiting the ED
- had they seen a neurologist prior to visiting the ED
- did they attend a follow up appointment
- did they have a Rx for triptans prior to visiting the ED
- did they have a Rx for opioids prior to visiting the ED

PMR: The RV or RA will explain the rationale for PMR and the APP will be uploaded onto the subjects' smartphones. The subject will perform PMR in the ED and discuss the optimal time and place to practice PMR at home.

Subjects will also enter their headache log daily on the APP. The APP will track the amount of time playing the PMR. Subjects will be asked to do the following:

Intervention:

Week 1: 5 min deep breathing at least 5/7 days of the week

Week 2: 5 min PMR session at least 5/7 days of the week

Week 3: 15 min pmr preferred at least 5/7 days of the week

Week 4: pmr at least 4 days a week (optional body scan)

Week 5: pmr at least 3 days a week (optional body scan)

Weeks 6-8: use when it is most helpful (falling asleep, HA coming on, stress)

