The study intervention will be 8 weeks in duration but the full study length will be 6 months. There will be a baseline assessment (T0), a f/u call or email at one week (T1), a 30 day phone call or email assessment (T2), a 60 day phone call/email (T3), and a 90 day phone call/email (T4) (to examine persistence of effect after a month). The last follow-up will be at 6 months to examine persistence of effect 4 months after the intervention ends. As we learned previously, we are adding the option for email as some subjects prefer email.

MUC: To match the time spent with the designated study team member, subjects will be given a general education session consisting of basic migraine information, such as evidence-based ways to treat headaches: treat early, limit acute medications < 2–3 days/week, and call the primary care physician (PCP) if abortive medications are used more frequently. They will be shown a website:

<https://[name].wixsite.com/relaxahead> (to be renamed) The study team member will load the app onto the subject's smartphone but the PMR component will be blocked on the version of the app that the MUC subject receives.

Discharge Plans and Post-Discharge Plans for All Subjects: All subjects will receive written educational material about migraine. This is the standard information about migraine that is printed from Epic when patients are discharged from the ED with migraine. Subjects will be asked to follow-up with a PCP upon discharge from the ED and will be offered an appointment for this follow-up visit unless they have an appointment scheduled. Subjects without a PCP will be referred to a PCP. There will be emphasis on ensuring that the subjects understand the discharge information, which will include the diagnosis and both verbal and written instructions. Letters will be sent to PCPs informing them of the study and stating that they are to treat the subjects as they see fit.

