For the secondary outcome of number of headaches in 30 days, group sample sizes of 31 and 31 achieve 80% power to detect a difference of 1.42 assuming an SD of 2 in both groups with a significance level of 0.05 using a two-sided two-sample t-test. Potential non-normal distributions will be considered for the count data of the number of headaches and analyzed using nonparametric tests. A simulation-based sample size calculation was performed assuming Poisson distributions. The sample size of 31 per group has >80% power to detect the difference of 1.4 using a two-sided Mann-Whitney test at significance level 0.05 assuming a Poisson distribution with mean 2 in the control group.

Aim 2 Data Collection and analyses:

PHI will be maintained in a separate log maintained securely as described below under data security.

Symptoms Diary

On the smartphone application platform developed by IRODY (used by the NYUMC epilepsy group for ongoing IRB approved studies), subjects will be trained to keep records of headache occurrence, side effects, compliance and medicine changes on their mobile device. If a subject fails to consistently record their data, they will receive a call/text/email from the RV or RA to ensure compliance with data maintenance. Information prompted by the device will include:

1. Headaches (number, type, and dates)
2. Abortive and preventive migraine drug treatment
3. Concomitant medications
4. Episodes of non-compliance
5. Changes made to migraine medication treatment plan, if any, and reasons for the change
6. Adverse effects, including severity, seriousness, unexpectedness as part of pharmacovigilance
7. Mood and anxiety levels, stress and sleep
8. Healthcare utilization

The symptoms diary may be accessed via the mobile application only. The app also includes the following questionnaires: PROMIS for depression and anxiety, the Perceived Stress Scale, and the Insomnia Sleep Index.

The study team will not share the symptoms diary information with the subject's treating physician. However, subjects can elect to share their data with their treating physician independently.

In addition to the application, REDCap, a HIPAA Compliant research database system, generated emails, and telephone calls by the blinded RAs with data entered into REDCap will be used to collect the MSQv2 and the MIDAS. The PHI of the subjects will only be stored in REDCap. IRODY does not receive PHI in the app or log in process.

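### Subjects are randomized before baseline data are collected, and the supplied text does not withhold the arm until T0 is complete: an avoidable opportunity for bias in ΔMIDAS

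*Combined protocol and SAP*

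**What the plan says.** The order of enrolment is in Methods & Procedures, Aim 2: "Once consented, subjects will be randomized to PMR therapy or MUC". The research volunteer or assistant is next to gather "health histories (biologic variables) and baseline data in REDCap on an iPad", then put the app on the subject's phone and conduct the session. One role therefore takes baseline and delivers the arm-specific contact. The MUC paragraph shows that whoever loads the app must know the arm by then, since "the PMR component will be blocked on the version of the app that the MUC subject receives".

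Two statements bear on blinding. For subjects, the same section presents both groups as an addition to usual ED care and says: "At the end, they will be told that they will be informed which group they were in". For staff, Aim 2 Data Collection and analyses refers to REDCap, emails and "telephone calls by the blinded RAs with data entered into REDCap will be used to collect the MSQv2 and the MIDAS", without naming a time point.

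Under Measurements, MIDAS "measures disability over the past 3 months", and ΔMIDAS is "defined as the difference between MIDAS scores at 3 months and at baseline". Sample Size treats ΔMIDAS as the primary outcome, whereas the Aim 2 methods and Measurements name MSQv2. That conflict is a separate matter.

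**The concern.** Randomization makes the arms comparable in true pre-treatment status. It does not make the recorded baseline values comparable if they are recorded after the arm is known. MIDAS asks for recall over three months, so the answer can be influenced by how the question is put or by what the subject expects. Because baseline is subtracted in ΔMIDAS, an arm-related difference in how it is reported looks like a treatment effect, or hides one, depending on direction. More subjects do not shrink it. Adjusting for baseline reduces it without removing it.

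Baseline MSQv2 is exposed in the same way only if MSQv2 is analysed as change or with baseline as a covariate. The Aim 3 moderators are a lesser concern: baseline pain, and the Perceived Stress Scale and PROMIS measures if they are first completed in the app after it has been loaded.

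**Working it through.** **Sequence.** The steps as written are: (1) consent; (2) randomization; (3) health history and baseline data; (4) app loaded; (5) session. Steps 4 and 5 require the arm to be known. Step 3 follows step 2, and no supplied text says the assignment stays hidden during step 3 or that a different person performs it. The documents do not say when staff first learn the arm, so *may know* is the right strength. For remote enrolment they give electronic consent followed by a Webex visit, and do not say where randomization falls.

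**Inputs (Sample Size).** 31 per arm; SD of ΔMIDAS 5 to 7; design difference 5; two-sided α = 0.05; t-test.

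**Plan's own figure.** n = 2(1.960 + 0.842)² × 7²/5² = 30.8, so 31 per arm. Power at 31 is 80.3% by the normal approximation and 79.0% by the noncentral t. With 30% dropout, 62/0.70 = 88.6, so 89, against 90 planned. The figure reproduces with SD 7. SD 5 would need only 16 per arm by the same formula.

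**Effect of a shift.** Let b be the between-arm difference in mean reported baseline that is due to knowledge of the arm. The documents give no value for b, so the question is put in reverse: how large must b be to raise type I error from 5% to 10%? The 10% benchmark is my choice.

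- Unadjusted ΔMIDAS: bias = b and SE = SD × √(2/31), which is 1.270 (SD 5) or 1.778 (SD 7). With 60 degrees of freedom, 10% rejection needs a noncentrality of 0.663.
- b = 0.663 × 1.270 = 0.84 (SD 5); b = 0.663 × 1.778 = 1.18 (SD 7).
- Relative to the design difference: 0.84/5 = 17% and 1.18/5 = 24%.
- Measurements states that "A decrease of 3 points in the MIDAS score corresponds to a one day reduction in headache related disability per month", so these are 0.84/3 = 0.28 and 1.18/3 = 0.39 days per month.
- With all 90 retained (45 per arm) the thresholds fall to 0.70 and 0.97.

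**Baseline-adjusted analysis.** Assume equal SDs at the two times and a baseline to 3-month correlation r (not in the documents). Then bias = r × b and residual SD = SD × √((1 + r)/2).

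| r (assumed) | b for 10%, SD 5 | b for 10%, SD 7 |
|---|---|---|
| 0.3 | 2.26 | 3.17 |
| 0.5 | 1.46 | 2.04 |
| 0.7 | 1.11 | 1.55 |

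**Opposite direction.** A 1-point shift against PMR turns a true difference of 5 into an apparent 4. Power of the unadjusted test falls from 79.0% to 60.0% (SD 7) or from 97.2% to 87.3% (SD 5).

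**No baseline in the analysis.** A 3-month score compared directly between arms does not contain b, so its type I error is unchanged.

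**The case against.** The strongest reply is that the route to bias is narrow. MIDAS and MSQv2 are patient-reported, and entry on an iPad is compatible with subjects completing them unaided. Subjects hear both arms described as an enhancement, and within the sentence baseline data come before the app and the session. The named primary outcome may not use baseline at all. The text is an addendum to a main protocol that was not supplied, and it relies on a Study Manual and training material that may fix the order of the visit. It is also a pilot.

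Much of this stands. Self-completion would reduce staff influence, but it is not stated: the text has staff collect the data. The wording to subjects partly mitigates the risk and does nothing to keep staff unaware. The order within a sentence is not concealment. The unseen documents may resolve the point, in which case the addendum still reads otherwise and needs aligning.

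A reader might infer that the blinded assistants in the data collection section contradict the enrolment sequence. The documents do not support that. Emails and telephone calls are the follow-up contacts elsewhere in the protocol, so that sentence most naturally describes follow-up. It does not conflict with the enrolment sequence, and it does not protect T0 either.

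**Conclusion.** The point holds as an avoidable opportunity for bias at T0. It rests on the stated order, on one role both taking baseline and delivering the arm, and on the absence of any supplied text that withholds allocation meanwhile. That MIDAS is among the baseline data is inferred from the definition of ΔMIDAS.

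The size is unknown. The thresholds of 0.84 to 1.18 points (unadjusted) and 1.11 to 3.17 points (adjusted, r from 0.7 to 0.3) say how much shift would matter; they are not evidence that any shift will occur. They concern ΔMIDAS only.

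Two stronger readings should be resisted. One is that baseline will be recorded unblinded and is therefore biased: the documents do not say when staff learn the arm. The other is that the primary outcome is compromised: a 3-month MSQv2 score compared without baseline is unaffected, and MSQv2 is the primary outcome named in the methods.

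No planned sample size changes. Minor priority for a pilot, worth doing because it costs so little.

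**What to change.** Rewrite the enrolment order as:

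1. consent;
2. complete the T0 battery (MSQv2, MIDAS, pain, baseline Perceived Stress Scale and PROMIS), self-completed where possible;
3. randomization, or reveal of an allocation already made;
4. the assigned app version and session.

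Use the same order within the Webex visit. State how the T0 questionnaires are completed, and say that the blinded assistants cover follow-up if that is the intent. If the main protocol or Study Manual already withholds allocation until T0 is complete, correct the addendum to match.

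The cost is a change of order within one visit. A few subjects may leave before being randomized, and baseline Perceived Stress Scale and PROMIS may need one REDCap entry because they otherwise sit in the app.

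### The plan states no pre-treatment value for MSQv2 (the primary outcome) or for headache frequency: T0 is scheduled but its contents are not listed

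*Combined protocol and SAP*

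**What the plan says.** **Order of enrollment.** Methods & Procedures states "Once consented, subjects will be randomized to PMR therapy or MUC". Staff then take the health history and "baseline data in REDCap on an iPad, download the app onto" the subject's phone, and hold the session. So baseline data come after allocation, although they are listed before the app and the session.

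**Baseline visit.** The schedule in the same section says "There will be a baseline assessment (T0), a f/u call or email at one week (T1"), followed by the later contacts. Neither place names the T0 instruments.

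**MSQv2.** The Aim 2 text reads "The primary outcome is to assess whether use of PMR in the ED improves migraine quality of life (MSQv2) at 3 months". For the 1, 2, 3 and 6 month contacts, "they will be asked to complete the REDCap follow-up questionnaires (already part of the IRB submission with the added modification of the MSQv2"). This is the only place where MSQv2 is tied to time points of collection other than the 3-month endpoint itself. Two other mentions give no time: all 90 subjects complete a quality-of-life assessment (Methods & Procedures, Aim 2), and MSQv2 is collected through REDCap together with MIDAS (Aim 2 Data Collection and analyses).

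**Headache frequency.** The sample-size text sets out a calculation "For the secondary outcome of number of headaches in 30 days". Headaches are logged daily on the app, and the Symptoms Diary text says the diary is reachable only through the app. Before treatment, frequency appears only as an entry threshold of 4 or more headache days a month (Inclusion Criteria).

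**MIDAS.** The Measurements paragraph defines its change score as 3 months against baseline. It is the only one of the three outcomes with a named baseline.

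**The concern.** The primary question is worded as improvement, and Aim 2 also asks about headache frequency. As written, the plan does not say that either is measured before treatment. A diary count cannot exist before randomization, because the app is not yet on the phone and no run-in is described. For MSQv2, a team building forms from this text would put it in the follow-up questionnaires and might leave it out of T0.

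A pre-treatment score not taken at T0 cannot be obtained later. Three things would then be missing: the precision gained by adjusting for the baseline, a check that the arms were alike on these outcomes, and a description of how far subjects moved. In a trial planned around 31 evaluable subjects per arm, the precision matters most.

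**Working it through.** **Inputs from the plan (Sample Size):** 31 per arm, two-sided alpha 0.05, 80% power; headache count difference 1.42, SD 2; dropout 30%; total 90.
**Assumed:** the baseline-to-follow-up correlation r is not in the documents, so 0.3, 0.5 and 0.7 are used. A baseline frequency SD of 5 is also assumed, as an upper illustration.

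**1. The plan's own figure.** Normal approximation: n = 2 × (1.960 + 0.842)² × 2² / 1.42² = 31.1, which rounds up to 32 per arm (32.1 with the t distribution). Power at 31 per arm is 79.8% (normal) or 78.5% (t). The stated 31 and 80% therefore reproduce to rounding. Dropout: 62 / 0.7 = 88.6, consistent with 90. This calculation uses follow-up values only and needs no baseline. The section contains no calculation for MSQv2, so results for that outcome are given in SD units.

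**2. Gain from a baseline covariate.** With adjustment for baseline in a linear model, the residual SD is SD × sqrt(1 − r²). The one degree of freedom spent on the covariate is ignored. The no-baseline detectable difference in the last column is 0.723 SD before rounding.

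| r | sqrt(1 − r²) | Residual SD (from 2) | Power for 1.42 headaches | Detectable difference, any outcome |
|---|---|---|---|---|
| no baseline | 1 | 2.00 | 78.5% | 0.72 SD |
| 0.3 | 0.954 | 1.91 | 82% | 0.69 SD |
| 0.5 | 0.866 | 1.73 | 89% | 0.63 SD |
| 0.7 | 0.714 | 1.43 | 97% | 0.52 SD |

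In headaches, 1.42 × sqrt(1 − r²) gives 1.35, 1.23 and 1.01.

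**3. Covariate or change score.** A change score has SD 2 × sqrt(2(1 − r)) if both occasions have SD 2. At r = 0.3 this is 2.37 and power for 1.42 is 64%. At r = 0.5 it is 2.00 and power is 78.5%, no better than having no baseline. The gain comes from adjustment, not from subtraction.

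**4. Chance imbalance in baseline frequency.** The SD of the difference between arm means is SD × sqrt(2/31) = SD × 0.254.
- SD 2 (the plan's follow-up figure, if it also held at baseline): 0.51, or 0.51 / 1.42 = 36% of the target difference.
- SD 5 (assumed; entry has no upper frequency limit): 1.27, or 1.27 / 1.42 = 89%.

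With equal SDs at the two times, only the fraction r carries into follow-up: at r = 0.5 to 0.7, 0.51 becomes 0.26 to 0.36, and 1.27 becomes 0.64 to 0.89.

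**The case against.** The strongest reply is that silence is not absence. T0 is scheduled, baseline data are collected in REDCap, and MSQv2 is paired with MIDAS, which does have a baseline. The document is an addendum: the main protocol, the Study Manual and the questionnaires are referred to but not reproduced, and T0 may already contain MSQv2. A paragraph about follow-up calls would not be expected to list T0 content. This stands in part. It rules out saying that a baseline is absent, but it does not supply the missing specification. It also does not help the diary, which cannot precede the app.

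A reader might infer more than the documents support:

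- **That spontaneous improvement after an ED visit could not be told apart from a treatment effect.** The randomized MUC arm does this, because such improvement is expected in both arms. A baseline taken at a bad moment would leave within-arm change affected by the same regression to the mean.
- **That chance imbalance would invalidate the comparison.** It is already allowed for in the standard error and alpha. Adjustment would reduce it, not repair a bias.
- **That Aim 3 fails.** Its stated hypothesis concerns migraine disability, for which MIDAS has a baseline. Its predictors are baseline pain, stress, anxiety and depression, not headache frequency.
- **That starting the diary after randomization is itself a bias.** It is not. A smaller point does hold: questionnaires answered after allocation could be influenced if the subject or the staff member knows the arm.

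The study calls itself a pilot, and baseline MIDAS gives one pre-treatment severity measure for checking balance. Both points lower the stakes without removing them.

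**Conclusion.** The point holds as a gap in specification. Neither MSQv2 nor headache frequency has a stated pre-treatment value, and baseline data are placed after randomization. The 3-month comparison between arms is valid without a baseline, and the headache sample size is built that way.

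The size of the loss depends on r, which the documents do not give. It is modest at 0.3 and substantial at 0.7. For the headache count, where baseline would be recalled and follow-up recorded by diary, the lower part of the range is the safer expectation. MSQv2 would use the same instrument at both times. The imbalance range of 0.51 to 1.27 rests on the assumed baseline SD, and the upper value is illustrative only. The change is worth making while T0 values can still be collected.

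**What to change.** 1. List the T0 instruments in the plan. Include MSQv2 and two numeric fields: headaches and headache days in the 30 days before enrollment. The documents do not say how the entry criterion on headache days is ascertained, so the numeric fields need to be stated explicitly.
2. Place T0 after consent and before randomization, for both ED and remote enrollment.
3. State that the 3-month MSQv2 and headache-count comparisons are adjusted for the matching baseline value in a regression model. The t-test and Mann-Whitney test named in Sample Size take no covariate.
4. Use the recalled count as a covariate only. Do not subtract it from diary counts.

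**Cost:** one questionnaire and two fields, a few minutes per subject, with no diary run-in and no delay to treatment. The baseline count will carry recall error, which reduces the gain in precision. If the existing T0 form already contains MSQv2, only the headache fields, the timing and the adjustment remain to be added.
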